9.1 Subject Confidentiality

All participants are concerned for the individual subject's privacy and, therefore, all subject data will be identified only by a subject identification number and subject initials. However, in compliance with federal guidelines regarding the monitoring of clinical studies and in fulfillment of his/her obligations to Perrigo, it is required that the investigator permit the study monitor, any Perrigo authorized representative, and/or FDA representative to review that portion of the subject's medical record that is directly related to the study. This shall include all study relevant documentation including subject medical histories to verify eligibility, laboratory test result reports to verify transcription accuracy, admission/discharge summaries for hospital stays occurring while the subject is enrolled in the study and autopsy reports for deaths occurring during the study.

As part of the required content of informed consent, the subject must be informed that his/her medical chart may be reviewed by Perrigo or their authorized representative, or a representative of the FDA. Should access to the medical record require a separate waiver or authorization, it is the investigator's responsibility to obtain such permission from the subject in writing before the subject is entered into the study.

To preserve the subject's confidentiality, the data collected will be available only to the investigators of the study, their support staff, Perrigo or their authorized representative and possibly the FDA.

All reports and communications relating to the subject in the study will identify each subject only by the subject's initials and by the subject number. The investigator agrees to furnish Perrigo with complete subject identification, if necessary on a confidential follow-up form, which will be used for the purpose of a long-term follow-up, if needed. This will be treated with strict adherence to professional standards of confidentiality and will be filed at Perrigo under adequate security and restricted accessibility.

10. CONDUCT OF STUDY

The investigational site is to maintain complete documentation of all events and the times at which they occur.

10.1 Completion of Study

The investigational site will complete the study and complete all documentation required, in satisfactory compliance with the protocol, within 3.5 months of enrollment of the last subject and extending beyond as needed to complete necessary data queries.

Protocol No: PRG-NY-17-008

It is agreed that, for reasonable cause, either the investigator or Perrigo may terminate this study before completion provided written notice is submitted at a reasonable time in advance of intended termination. Any extension of this study must be mutually agreed upon in writing by both the investigator and Perrigo.

10.2 Protocol Amendments

The Investigator will not make any changes to this protocol without prior written consent from Perrigo and subsequent approval by the IRB. Any permanent change to the protocol, whether it is an overall change or a change for specific study center(s), must be handled as a protocol amendment. Any amendment to the protocol that appears indicated as the study progresses will be fully discussed between [REDACTED] and Perrigo. If agreement is reached regarding the need for an amendment, the amendment will be written by Perrigo. The written amendment must be submitted to the chairman of the IRB identified with this responsibility. Except for ‘administrative amendments’, investigators must await IRB approval of protocol amendments before implementing the change(s). Administrative amendments are defined to have no effect on the safety of the research subjects, scope of the investigation, or quality of the trial. However, a protocol change intended to eliminate an apparent immediate hazard to subjects should be implemented immediately, and the IRB notified within five days. Perrigo will submit protocol amendments to the FDA or other regulatory agencies.

When, in the judgment of the reviewing IRB, the investigators and/or Perrigo, the amendment to the protocol substantially alters the study design and/or increases the potential risk to the subject, the currently approved written informed consent form will require similar modification. In such cases, repeat informed consent will be obtained from subjects enrolled in the study before expecting continued participation.

11. RECORDS MANAGEMENT

11.1 Data Collection

Database set-up will be performed by [REDACTED] in collaboration with the Electronic Data Capture (EDC) vendor, using an appropriate fully validated, 21 CFR Part 11 compliant EDC system. eCRFs will be provided to each site via a secured web link. All applicable study data collected on each subject will be recorded by approved site personnel into the eCRF. Only authorized site personnel will be able to enter/modify/correct data to the eCRF.

Approved staff at [REDACTED] will verify all data entered into eCRFs for completeness and accuracy with reference to the source documents and records and will issue manual data queries to correct missing data or discrepancies found against the source within the EDC system.

Data validation will consist of automated and manual edit checks that are created directly into EDC. Automated edit checks will be executed on all data points defined and documented by the study team and data management. Study metrics will be reported from the EDC system.

Protocol No: PRG-NY-17-008

After all data have been verified by approved staff at [REDACTED] an Investigator or Sub-Investigator (listed on Form FDA 1572) is required to review and approve all eCRFs prior to database lock and breaking of the blind.

After database lock, each site will be provided with a password protected CD that will include the eCRF data from their site for local archival purposes.

Quality assurance verification via a 10% database audit of eCRF data will be conducted before the treatment assignment code is broken.

During each subject's visit to the clinic, a designee participating in the study will record progress notes to document all significant observations. At a minimum, these notes will contain:

- a) Documentation of the informed consent process;
- b) The date of the visit and the corresponding Visit or Week in the study schedule;
- c) General subject status remarks, including any significant medical findings. The severity, frequency, and duration of any adverse events and the investigator's assessment of relationship to study medication must also be recorded.
- d) Any changes in concomitant medications or dosages;
- e) A general reference to the procedures completed; and
- f) The signature (or initials) and date of all clinicians who made an entry in the progress notes.

In addition, any contact with the subject via telephone or other means that provides significant clinical information will also be documented in the progress notes as described above.

Any changes to information in the study progress notes and other source documents, will be entered in **black or blue ink, initialed and dated** by the authorized person making the correction/addition. Changes will be made by striking a single line through erroneous data, and clearly entering the correct data. (e.g., ~~wrong data~~ right data). Entries may not be erased or masked with white-out fluid. If the reason for the change is not apparent, a brief explanation for the change will be written adjacent to the change by the clinician.

For transmission to Perrigo, information from the study progress notes and other source documents will be promptly entered into the database. The database also contains a complete audit trail to capture all regulatory components of data corrections (e.g. initial entry, new value, initials and date of the change).

11.2 Source Documents

Source documents are defined as the results of original observations and activities of a clinical investigation. Source documents will include, but are not limited to, progress notes and screening logs. All source documents pertaining to this study will be maintained by the investigators and made available for inspection by authorized persons. The original signed informed consent form for each participating subject shall be filed with records kept by the investigators and a copy given to the subject.

11.3 File Management at the Study Site

It is the responsibility of the investigator to ensure that the study center file is maintained in accordance with Section 8 of the International Conference on Harmonization (ICH) Guideline for Good Clinical Practices (GCP).

11.4 Records Retention at the Study Site

FDA regulations 21 CFR§312.57 require all investigators participating in clinical drug studies to maintain detailed clinical data for one of the following periods:

- a) A period of at least two years following the date on which a New Drug Application is approved by the FDA;
- b) A period of two years after Perrigo notifies the investigator that no further application is to be filed with the FDA.

The investigator must not dispose of any records relevant to this study without either (1) written permission from Perrigo or (2) providing an opportunity for Perrigo to collect such records. The investigator shall take responsibility for maintaining adequate and accurate electronic or hard copy source documents of all observations and data generated during this study. Such documentation is subject to inspection by Perrigo and the FDA.

12. QUALITY CONTROL AND QUALITY ASSURANCE

12.1 Monitoring

Perrigo has ethical, legal and scientific obligations to carefully follow this study in a detailed and orderly manner in accordance with established research principles and FDA regulations. All medical records (source documents) of the subjects participating in this study must be presented for review and verification of eCRFs.

12.2 Auditing

Perrigo (or representative) may conduct audits at the study center(s). Audits will include, but are not be limited to, drug supply, presence of required documents, the informed consent process, and comparison of electronic case report forms with source documents. The investigator agrees to participate with audits conducted at a reasonable time in a reasonable manner.

Regulatory authorities worldwide may also audit the investigator during or after the study. The investigator should contact Perrigo immediately if notified of such an audit, and must fully cooperate with the audits conducted at a reasonable time in a reasonable manner.

13. ETHICS AND RESPONSIBILITY

This study must be conducted in compliance with the protocol, the United States Food and Drug Administration (FDA) regulations, any other countries regulations, and ICH GCP Guidelines.

The purpose of the statistical analysis plan is to describe in detail all the data, statistical methods, and summary tables required to implement the statistical analysis of Clinical Study Protocol PRG-NY-17-008 [REDACTED]
[REDACTED]

2 Study Objectives

To compare the safety and efficacy profiles of Perrigo UK FINCO's Limited Partnership Adapalene and Benzoyl Peroxide Topical Gel, 0.3%/2.5% to Galderma Laboratories Epiduo[®] Forte (Adapalene and Benzoyl Peroxide) Gel, 0.3%/2.5%, in order to prove bioequivalence between them and to demonstrate the superior efficacy of the two active formulations over that of the vehicle in the treatment of Acne Vulgaris.

3 Study Design and Sample Size

3.1 Study Design

For the purpose of exploring the above objectives, the study will be conducted as a double-blind, randomized, parallel-group, vehicle-controlled, multicenter trial.

Each subject will be randomly assigned to one of the following treatment groups [REDACTED]
[REDACTED]

- (1) Test: Adapalene and Benzoyl Peroxide Topical Gel, 0.3%/2.5%, Perrigo UK FINCO Limited Partnership, [REDACTED]
- (2) Reference: Epiduo[®] Forte (Adapalene and Benzoyl Peroxide) Gel, 0.3%/2.5%, manufactured by Galderma Laboratories, L.P.
- (3) Vehicle of test product, [REDACTED].

Subjects will be admitted into the study only after written informed consent has been obtained and all of the inclusion and none of the exclusion criteria have been met. Male and female subjects 12 years to 40 years of age, inclusive, with acne vulgaris [REDACTED] will be eligible for enrollment. Randomization will be performed according to a computer generated randomization scheme where the treatment group designation has been assigned to the subject number. The treatment designation will remain blinded until after the final database is locked. An independent third party will generate and hold the randomization code throughout the study. Randomized subjects will apply [REDACTED] the study medication onto each area of the face (forehead, chin, right cheek, left cheek and nose) [REDACTED] avoiding contact with the eyes, lips, inside your nose/nostrils, angles of the nose, broken skin areas and mucous membranes at approximately the same time once daily for 12 weeks.

Subjects will come to the study site for clinical evaluations Visit 1/Day 1 (Baseline), Visit 2/Interim/Week 4 (Day 28 ±4 days), Visit 3/Interim/Week 8 (Day 56 ±4 days), and Visit

4/End of Treatment/ Week 12 Study (Day 84 ±4 days) or at early discontinuation. Safety will be assessed by monitoring adverse events at each visit and at the Week 2/Day 14 (±4 days) Telephone Contact.

3.2 Sample Size

[REDACTED]

[REDACTED]

[REDACTED]

[figure not shown]
4 Populations To Be Analyzed

The analysis populations are defined as follows:

- (1) Intent-to-treat (ITT) population: any subject that was randomized, received and used study medication;
- (2) Modified Intent-to-treat (mITT) population: any subject, who met the inclusion/exclusion criteria, was randomized, received and used the study medication, and returned for at least one post-baseline efficacy assessment;
- (3) Per Protocol (PP) population: any subject who (a) met all inclusion/exclusion criteria; (b) was randomized and received and used study medication; (c) met the protocol criteria for compliance [REDACTED] (d) completed Visit 4/Week 12/Day 84 (End of Treatment/Early Termination Visit) efficacy

evaluations within window (± 4 days) OR was discontinued from the study due to treatment failure and; (e) Without significant protocol violations that could have interfered with the administration of the treatment or the precise evaluation of treatment efficacy.

5 Planned Analyses

5.1 Methodological Considerations

The study will be conducted under the same protocol across all the sites. No formal statistical analyses are planned to evaluate the consistency of efficacy results across the multiple clinical sites. These results, however, will be tabulated and if a site's efficacy data are obviously inconsistent with the results across all sites, this will be explored and addressed in the final study report.

All randomized subjects who received study medication will be evaluated for safety using ITT population. The efficacy analysis will be conducted on both the PP and the mITT populations.

Two-sided hypothesis testing will be conducted for all the tests. Resulting p-values less than 0.05 will be considered statistically significant unless noted otherwise. No adjustments of p-values for multiple comparisons will be made. No interim analyses are planned.

SAS software will be used for all data analyses and tabulations.

5.2 Handling of Dropouts or Missing Data

For demographic and baseline characteristics and the safety profile, each variable will be analyzed using all available data. Subjects with missing data will be excluded only from the analyses for which data are not available.

5.3 Demographics and Baseline Characteristics

Baseline variables (e.g., sex, age, ethnic origin) will be summarized descriptively by treatment group and evaluated, adjusting for site, to identify differences between treatment groups, which were not eliminated by randomization. Any significant baseline differences will be reviewed for their potential impact on the efficacy findings.

Continuous variable at baseline will be examined by two-way analysis of variance (ANOVA) with treatment and site as fixed effects when normal error and homogeneous variance assumptions are satisfied, or by non-parametric rank based ANOVA when they are not, to compare treatment group differences. The summary tables will include the mean, standard deviation, minimum and maximum. For each categorical variable, the summary will include frequencies and percentages and be examined by Cochran-Mantel-Haenszel test and stratified by site.

5.4 Subject Accountability

A summary of subject disposition will be provided for all subjects. Descriptive summaries of subject disposition, reason for discontinuation, and analyses population will be provided by treatment group. The data will also be presented in subject data listings.

5.5 Efficacy Variables and Analyses

5.5.1 Primary Endpoint

The two primary efficacy endpoints are the mean percent change from baseline to Visit 4/Week 12/Day 84 in the inflammatory (papules and pustules) lesion counts AND the mean percent change from baseline to Visit 4/Week 12/Day 84 in the non-inflammatory (open and closed) lesion counts.

Equivalent Efficacy

For the mean percent change from baseline in the inflammatory lesion counts, the Test treatment will be considered to be therapeutically equivalent to the Reference treatment if the 90% confidence interval on the Test-to-Reference ratio of means, calculated by Fieller's Method, falls within the interval 0.80 to 1.25. The compound hypothesis to be tested for therapeutic equivalence between test and reference is:

$$H_0: \mu_T / \mu_R \leq 0.80 \text{ or } \mu_T / \mu_R \geq 1.25 \text{ versus}$$

$$H_A: 0.80 < \mu_T / \mu_R < 1.25.$$

Where μ_T and μ_R are the mean percent change from baseline to Visit 4/Week 12/Day 84 in inflammatory lesions counts for the test treatment and the reference treatments, respectively.

The null hypothesis is rejected when the two-sided 90% confidence interval (CI) for the ratio of means between test and reference products is between 0.80 and 1.25. Rejection of the null hypothesis supports the conclusion of therapeutic equivalence between test and reference products for the primary efficacy variable.

The two-sided 90% confidence interval will be constructed using an ANOVA model with treatment and site as factors. [REDACTED]

The same analysis will be applied to the mean percent change from baseline in the non-inflammatory lesion counts.

[REDACTED]

Analysis for therapeutic equivalence will be performed based on the following SAS code (SAS Institute v.9.4), e.g. trt=1 for Test and trt=2 for Reference:

[REDACTED]

Where the ESTIMATE statement is run targeting at two-sided $p=0.10$ to locate the c value (our Test/RLD) for the 90% CI.

Superiority

For the mean percent change from baseline in the inflammatory lesion counts, each active treatment will be evaluated to determine if it has superior efficacy to that of the Vehicle at Visit 4/Week 12/Day 84 via an ANOVA model containing terms for treatment and site. The compound hypothesis to be tested for superiority of test and reference over Vehicle is:

$$H_0 : \mu_T \leq \mu_V \text{ or } \mu_R \leq \mu_V \text{ versus}$$

$$H_A : \mu_T > \mu_V \text{ and } \mu_R > \mu_V$$

Where μ_T , μ_R and μ_V are the mean percent change from baseline to Visit 4/Week 12/Day 84 in inflammatory lesions counts for the test, the reference and the vehicle treatments, respectively. The null hypothesis is rejected when both p -values from the ANOVA are less than 0.05 (two-sided test). Rejection of the null hypothesis supports the conclusion of superiority of test and reference products over the vehicle product for the primary efficacy variable.

[REDACTED]

The same analysis will be applied to the mean percent change from baseline in the non-inflammatory lesion counts.

[REDACTED]

Analysis for superiority will be performed based on the following SAS code (SAS Institute v.9.4), e.g. trt=2 for Reference vs. trt=3 for Placebo:

[REDACTED]

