5.13 Summary of Assessments

The schedule of visits and procedures to be conducted at each visit are summarized in the Schedule of Study Procedures.

The following procedures: Informed Consent, Inclusion/Exclusion Criteria, Medical History/Demographics, collection and review of Concomitant medications, Physical exam, Vital signs, dermatological assessment (diagnosis), lesion counting, IGA, and Urine pregnancy test must be completed and documented on the source document before a subject is randomized on the study.

[REDACTED]

[REDACTED]

[REDACTED]

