8.1.4 Efficacy Measures and Analysis

Clinical endpoints

The primary efficacy measure will be the mean percent change from baseline to Visit 4/Day 84/Week 12 in the inflammatory (papules and pustules) lesion counts AND the mean percent change from baseline to Visit 4/Day 84/Week 12 in the non-inflammatory (open and closed) lesion counts. The secondary efficacy measure will be the proportion of subjects with clinical success on the Investigator's Global Assessment (IGA) at Visit 4/Day 84/Week 12. Success is defined as an IGA score that is at least 2 grades less than the baseline assessment.

Equivalent efficacy

For the mean percent reduction from baseline in the inflammatory and non-inflammatory lesion counts, the Test treatment will be considered to be therapeutically equivalent to the Reference treatment if the 90% confidence interval on the Test-to-Reference ratio of means, calculated by Fieller's Method, falls within the interval 0.80 to 1.25. The treatment means and estimate of residual variance for the confidence interval calculation will come from an Analysis of Variance of the Test and Reference results using a statistical model containing terms for Treatment and Site.

For the proportion of subjects with clinical success, the Test treatment will be considered to be therapeutically equivalent to the Reference treatment if the 90% confidence interval on the difference between Test and the Reference proportions is contained within the interval -20% to +20%. The confidence interval will be constructed using Wald's method with Yates' continuity correction.

Superiority

For the percent reductions from baseline in the inflammatory and non-inflammatory lesion counts, each active treatment will be evaluated to determine if it has superior efficacy to that of the Vehicle at Visit 4/Week 12/Day 84 via an Analysis of Variance using a statistical model containing terms for Treatment and Site.

The proportion of subjects with clinical success for each active treatment will be compared to that of the Vehicle using a Z-test with Yates' continuity correction.

All hypothesis tests will be two-sided at a significance level of $\alpha = 0.05$, except confidence intervals which will be based on $\alpha = 0.1$ (e.g., 90% coverage).

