8.2 Comparability of Subjects at Baseline

Descriptive statistics will be presented, by treatment group, for subject baseline characteristics. The significance of any obvious treatment group differences will be discussed in the CSR.

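### Optional improvement: the visible primary lesion-count models use treatment and site only; the baseline count of the same lesion type could be pre-specified as a centred covariate

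*SAP*

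**What the plan says.** **Model.** SAP 5.5.1 (Equivalent Efficacy) states that the two-sided 90% "confidence interval will be constructed using an ANOVA model with treatment and site as factors". Protocol 8.1.4 agrees: the treatment means and the residual variance for the Fieller interval "will come from an Analysis of Variance of the Test and Reference results using a statistical model containing terms for Treatment and Site". In SAP 5.5.1 superiority over vehicle is assessed "via an ANOVA model containing terms for treatment and site". The non-inflammatory count is analysed in the same way as the inflammatory count.

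**Ratio limits.** An ESTIMATE statement is run "to locate the c value (our Test/RLD) for the 90% CI". The interval must lie within 0.80 to 1.25.

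**Baseline data.** Protocol 5.13 lists the procedures that precede randomization and ends the list with "lesion counting, IGA, and Urine pregnancy test must be completed and documented on the source document before a subject is randomized on the study".

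**Baseline imbalance.** SAP 5.3 compares the arms at baseline, adjusting for site, and adds: "Any significant baseline differences will be reviewed for their potential impact on the efficacy findings". Protocol 8.2 says: "Descriptive statistics will be presented, by treatment group, for subject baseline characteristics". Neither section names an adjusted efficacy analysis.

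**Not visible.** Text is blacked out at the end of Protocol 8.1.2, directly after the equivalence model sentence, around the superiority paragraphs, in all the SAS code and in SAP 5.5.3. Sample size, SD and power are also blacked out (Protocol 8.1.3, SAP 3.2).

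**The concern.** A covariate measured before randomization can be put in the model without harming validity, and it removes outcome variance in proportion to r². Here the count is already collected, and the width of the Fieller interval follows the residual variance, so an unused predictor of outcome leaves the interval slightly wider than it need be for each of the two primary endpoints.

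In the visible text, a chance imbalance in baseline count is dealt with only by review after the data are in, and nothing states what follows from that review. A covariate fixed in advance would give a rule for this one variable.

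**Working it through.** No stated figure can be reproduced, because sample size, SD, allocation and power are blacked out. Everything below is illustrative, for one lesion type. Reductions are taken as positive.

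**Inputs from the documents:** model terms treatment and site; equivalence limits 0.80 and 1.25; 90% interval.

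**Assumed inputs:** Reference mean reduction 55; true ratio 0.95, so Test mean 52.25; SD 40; n = 200 per active arm; 10 sites; |r| from 0 to 0.3.

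**Step 1: variance.** Adjusted variance = SD² × (1 − r²). The interval width scales with √(1 − r²).

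| \|r\| | variance removed | width factor |
|---|---|---|
| 0 | 0% | 1.000 |
| 0.1 | 1% | 0.995 |
| 0.2 | 4% | 0.980 |
| 0.3 | 9% | 0.954 |

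Only r² enters, so the sign of r does not matter here.

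**Step 2: equivalence power, planned model.** The Fieller interval lies within the limits when T − 0.80R and 1.25R − T are both significantly above zero, one-sided at 5%. The critical t is 1.649 (389 degrees of freedom).

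- Lower: 52.25 − 44 = 8.25; SE = 40 × √(1.64/200) = 3.622; 8.25/3.622 − 1.649 = 0.629; probability 0.735.
- Upper: 68.75 − 52.25 = 16.5; SE = 40 × √(2.5625/200) = 4.528; 16.5/4.528 − 1.649 = 1.995; probability 0.977.
- The two statistics correlate at −0.976, so joint power is close to 0.735 + 0.977 − 1 = 0.712.

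**Step 3: with the covariate, |r| = 0.2.** SD becomes 40 × √0.96 = 39.19, and the SEs become 3.549 and 4.436. The margins are 0.676 and 2.071, with probabilities 0.750 and 0.981. Power is 0.731. The same steps give 71.7% at |r| = 0.1 and 75.5% at |r| = 0.3.

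**Step 4: range.** Over n = 150 to 400 per arm, SD 35 to 45 and true ratio 0.95 or 1.00, the gain in percentage points is 0.0 at r = 0, 0.0 to 0.7 at 0.1, 0.03 to 3.0 at 0.2 and 0.1 to 6.8 at 0.3. It is smallest where power is already high: at n = 300, SD 40, ratio 1.00 and |r| = 0.2, power moves from 96.2% to 96.8%.

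**Step 5: simulation of the same example.** Planned against adjusted power is 71.4% and 71.2% at r = 0, 71.1% and 73.3% at r = +0.2, and 70.9% and 72.8% at r = −0.2. The gain therefore holds for either sign, and the cost at r = 0 is about 0.2 point. Type I error at ratios 0.80 and 1.25 (checked at r = 0 and 0.2) was 4.7% to 5.3% under both models.

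**Step 6: why centring matters.** A ratio of adjusted means depends on the baseline count at which it is evaluated; a difference does not. Assume a baseline mean of 30 and SD of 12. The slope is r × 40/12, which is ±0.667 at r = ±0.2. Evaluated at a count of 0, each arm mean shifts by −30 × slope:

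- r = +0.2: (52.25 − 20)/(55 − 20) = 32.25/35 = 0.921.
- r = −0.2: (52.25 + 20)/(55 + 20) = 72.25/75 = 0.963.

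The true ratio at the mean baseline is 0.95. An uncentred contrast is therefore biased, in a direction set by the sign of r. In simulation its chance of meeting the limits was about 15% at r = +0.2 and about 95% at r = −0.2.

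**The case against.** The strongest case against is that nothing needs repair. Protocol and SAP agree on a pre-specified model that holds its error rate, the endpoint already divides by baseline, and site is in the model. The size of any benefit rests on r, N and SD, none of which is visible; at |r| = 0.1 it is under one point. A plain T − c·R contrast needs no covariate value, so the covariate also introduces a coding risk. All of this stands. It limits the point to an option.

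Three stronger readings are tempting, and the documents do not support them.

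- **That the plan ignores baseline lesion counts.** SAP 5.3 gives sex, age and ethnic origin only as examples and then covers continuous baseline variables by ANOVA with treatment and site. Lesion counts plausibly fall under that. The covariate would supplement this review, which spans all baseline variables, and would not replace it.
- **That imbalances too small to be flagged as significant undermine the equivalence result.** Grouping trials by their baseline imbalance does show power rising in one direction and falling in the other. But this only divides up sampling error that the 90% interval already covers. Which direction is harmed depends on the sign of r, which is unknown.
- **That no adjusted analysis is planned.** The blacked-out text prevents that conclusion. Protocol 8.1.4 does show that the primary model is treatment and site, but a supportive adjusted analysis may exist.

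**Conclusion.** The visible primary models for both lesion types contain treatment and site only, and a valid pre-randomization covariate is left unused. This is an optional, low-cost improvement to a sound analysis. A reader might infer that the planned interval is biased or invalid; it is neither.

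The gain is r² of the residual variance for either sign of r. In the assumed 200-per-arm case that is about 0.5, 2 or 4 points of power per lesion type at |r| = 0.1, 0.2 or 0.3, and none at r = 0. These figures rest on the assumed N, SD, mean reduction, true ratio and r. If r is close to zero, which is plausible for a percent-change endpoint, the change gains nothing and costs almost nothing. If the blacked-out text already specifies an adjusted analysis, confirmation settles the point.

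**What to change.** Before unblinding:

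1. Confirm whether the blacked-out parts of SAP 5.5.1 or 5.5.3 already adjust for the baseline count.
2. If not, specify treatment, site and baseline count of the same lesion type in SAP 5.5.1, for equivalence and superiority and for both lesion types.
3. For the ratio, centre the covariate at the pooled Test and Reference mean baseline count of the population analysed (mITT or PP), and state that T − c·R is evaluated there. For superiority the contrast is a difference, so the reference value cancels.
4. Keep the treatment-and-site ANOVA as a sensitivity analysis, and leave the SAP 5.3 review in place.
5. Align Protocol 8.1.4 with the SAP.

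The cost is one degree of freedom, one sentence giving the reference baseline value and a check of the ESTIMATE contrast. Because Protocol 8.1.4 states the model, an amendment may be needed: under Protocol 10.2 a permanent change "must be handled as a protocol amendment", with IRB approval unless it is administrative. No new data are needed, and endpoint, margin and sample size do not change.
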